- 8. Subjects with known genetic dermatological conditions that overlap with AD, such as Netherton syndrome.
- 9. Known allergies to excipients in ARQ-151 cream
- 10. Subjects who cannot discontinue the use of strong cytochrome P-450 CYP3A4 inhibitors e.g., indinavir, nelfinavir, ritonavir, clarithromycin, itraconazole, ketoconazole, nefazodone, saquinavir, suboxone and telithromycin for 2 weeks prior to Baseline/Day 1 and during the study period.
- 11. Subjects who cannot discontinue the use of strong cytochrome P-450 CYP3A4 inducers e.g., efavirenz, nevirapine, glucocorticoids, barbiturates (including phenobarbital), phenytoin, rifampin, and carbamazepine for 2 weeks prior to Baseline/ Day 1 and during the study period.
- 12. Subjects who have received oral roflumilast (Daxas®, Daliresp®) within 4 weeks prior to Baseline/ Day 1.
- 13. Known or suspected:
 - Severe renal insufficiency
 - Severe renal insufficiency is defined as calculated creatinine clearance <30 mL/min.
 - Moderate to severe hepatic disorders (Child-Pugh B or C)
- 14. History of severe depression, suicidal ideation or behavior, Baseline/Screening C-SSRS (for adolescents and adults 12 years

old and older) indicative of suicidal ideation or behavior,
whether lifetime or recent/current.

- 15. Subjects with a PHQ-8 (adults) or modified PHQ-A (adolescents, 12-17 years old inclusive) score ≥10 at Screening or Baseline/Day 1 visits.
- 16. Subjects (6 to 11 years old, inclusive) with a CDI-2 (parent report) raw score ≥17 for females and ≥18 for males at Screening or Baseline/Day 1 visits.
- 17. Females who are pregnant, wishing to become pregnant during the study, or are breast-feeding.
- 18. Previous treatment with ARQ-151.
- 19. Subjects currently undergoing allergy testing (e.g., food allergy testing or skin prick testing), patch testing, food challenges, or allergy desensitization, or plan to do so during the study.
- 20. Subjects with any serious medical condition (e.g., hypo- or hyper-thyroidism) or clinically significant laboratory abnormality that would prevent study participation or place the subject at significant risk, as determined by the Investigator.
- 21. Subjects with a history of a major surgery within 4 weeks prior to Baseline/Day 1 or subjects who have a major surgery planned during the study.
- 22. Subjects with a history of chronic alcohol or drug abuse within 6 months prior to Screening.

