2.3.7. Oral Roflumilast Tablet

Oral roflumilast (DALIRESP®) has been approved globally for the treatment of COPD and has been evaluated in nine Phase III/IV randomized double-blind clinical trials (Wedzicha 2016). Overall, the safety of oral roflumilast has been well established in its targeted population of mostly middle- and upper-aged individuals who currently smoke cigarettes or have smoked them extensively in the past. Adverse events (AEs) reported with roflumilast tablets have been consistent with those expected for oral PDE-4 inhibitors. In a pooled analysis of safety data from 6-month and 1-year clinical trials (N=8630), the most common AEs were diarrhea, weight loss and nausea. Other AEs reported more frequently with roflumilast treatment than with placebo were back pain, influenza, insomnia and decreased appetite (Michalsk, 2012), (Wedzicha, 2016).

In addition to the self-reported cases of weight loss in the 6-month and 1-year oral trials, clinically significant weight loss was also reported in two prospective studies that evaluated weight (Michalsk, 2012).

Psychiatric-related AEs were also greater in patients treated with roflumilast tablets (5.9%) compared to those treated with placebo (3.3%). The most common psychiatric-related AEs were insomnia, depression and anxiety. A small number of cases of completed suicide and suicide ideation have been reported in patients taking oral roflumilast in clinicals trials and also during post-marketing experience (Michalsk, 2012).

The only contraindication to oral roflumilast is use in patients with moderate to severe liver impairment (Child-Pugh B or C), where systemic levels of roflumilast may become elevated.

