- 11. Subjects who cannot discontinue the use of strong cytochrome P-450 CYP3A4 inducers e.g., efavirenz, nevirapine, glucocorticoids, barbiturates (including phenobarbital), phenytoin, rifampin, and carbamazepine for 2 weeks prior to the Baseline/Day 1 and during the study period.
- 12. Subjects who have received oral roflumilast (Daxas®, Daliresp®) within the past 4 weeks.
- 13. Known or suspected:
 - Severe renal insufficiency
 - Severe renal insufficiency is defined as calculated creatinine clearance <30 mL/min.
 - Moderate to severe hepatic disorders (Child-Pugh B or C)
- 14. History of severe depression, suicidal ideation or behavior, Baseline/Screening C-SSRS (for adolescents and adults 12 years old and older) indicative of suicidal ideation or behavior, whether lifetime or recent/current
- 15. Subjects with a PHQ-8 (adults) or modified PHQ-A (adolescents, 12-17 years old inclusive) score ≥10 at Screening or Baseline visits
- 16. Subjects (6 to 11 years old, inclusive) with a CDI-2 (parent report) raw score ≥17 for females and ≥18 for males at Screening or Baseline/Day 1 visits
- 17. Females who are pregnant, wishing to become pregnant during the study, or are breast-feeding.
- 18. Previous treatment with ARQ-151.

- 19. Subjects currently undergoing allergy testing (e.g., food allergy testing or skin prick testing), patch testing, food challenges, or allergy desensitization, or plan to do so during the study.
- 20. Subjects with any serious medical condition (e.g., hypo- or hyper-thyroidism) or clinically significant laboratory abnormality that would prevent study participation or place the subject at significant risk, as determined by the Investigator.
- 21. Subjects with a history of a major surgery within 4 weeks prior to Baseline/Day 1 or subjects who have a major surgery planned during the study.
- 22. Subjects with a history of chronic alcohol or drug abuse within 6 months prior to Screening.
- 23. Current or a history of cancer within 5 years with the exception of fully treated skin basal cell carcinoma, cutaneous squamous cell carcinoma or carcinoma in situ of the cervix.
- 24. Parent(s)/legal guardian(s) who are unable to communicate, read, or understand the local language. Subjects who are unable to communicate, read or understand the local language(s), or who display another condition, which in the Investigator's opinion, makes them unsuitable for clinical study participation.

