- DFI Score = sum of the 10 questions (individual questions scored as Very much=3, A lot=2, A little=1; Not at all=0), ranging from 0 to 30. If 1 item is missing, it is scored as 0 for that item. If 2 or more items are missing, the score should not be calculated.
- PHQ-8 = sum of the 8 questions (individual questions scored as Not at all=0, Several days=1, More than half the days=2, and Nearly every day=3), ranging from 0 to 24. If more than 1 item is missing the score should not be calculated. If 1 item is missing the score is calculated as (sum of answered items*8)/number of answered items (=7).
- Modified PHQ-A = sum of the 8 questions (individual questions scored as Not at all=0, Several days=1, More than half the days=2, and Nearly every day=3), ranging from 0 to 24. If more than 1 item is missing the score should not be calculated. If 1 item is missing, the score is calculated as (sum of answered items*8)/number of answered items (=7).
- CDI-2 total score is a sum of the 17 questions based on the scoring grid (individual questions scored as much or most of the time=0, often=1, some of the time=2, Not at all=3 for questions Q2, Q7, Q13, Q14, and Q16; individual questions scored as much or most of the time=3, often=2, some of the time=1, Not at all=0 for all other questions), ranging from

	STATISTICAL ANALYSIS PLAN, Version 3.0
Protocol Number: ARQ-151-311	Sponsor: Arcutis Biotherapeutics, Inc.

0 to 51. All CDI-2 raw scores can be prorated using the following formula, rounding to the nearest whole number:

- Prorated score = (Obtained raw score for scale) * (Total # of items on scale/subscale) / Total # items on scale/subscale with responses
- CDI-2 emotional problem scale is a sum of 9 questions (Q1, Q3-6, Q8, Q10-12). If more than 1 item is missing the score should not be calculated. If 1 item is missing the score is calculated as (sum of answered items*9)/number of answered items (=8).
- CDI-2 functional problem scale is a sum of 8 questions (Q2, Q7, Q9, Q13-17). If more than 1 item is missing the score should not be calculated. If 1 item is missing the score is calculated as (sum of answered items*8)/number of answered items (=7).

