13.4 Local Tolerability Assessments

The investigator's assessment of the application site reaction will be summarized by visit using both categorical methods (number and percentage of subject with each score) as well as continuous methods (e.g., mean, standard deviation, etc.)

Local tolerability (burning/stinging sensation) assessed by the subject will be summarized using number and percentage similarly.

13.5 Patient Health Questionnaire Depression Scale (PHQ-8) and Patient Health Questionnaire Depression Scale (Modified PHQ-A)

The Modified PHQ-A Assessment will be performed in adolescent subjects (12-17 years old, inclusive; question 9 has been removed since that is better evaluated by use of the C-SSRS tool).

The PHQ-8/Modified PHQ-A score is the sum of the responses for the questions, each question ranging from 0 (Not at all) to 3 – (Nearly every day). Five severity categories of depression are defined as follows:

- None – Minimal depression (0 to 4)
- Mild depression (5 to 9)
- Moderate depression (10 to 14)
- Moderately severe depression (15 to 19)
- Severe depression (20 to 24)

The score will be set to missing in case of at least one missing value. The number and percentage of subjects in each category will be summarized by treatment and visit. A summary of the shifts in depression category from baseline to each study visit will also be provided.

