13.6 Children's Depression Inventory 2 (CDI-2)

The CDI-2 Assessment will be performed in children subjects (6-11 years old, inclusive).

The observed values and changes from baseline will be calculated for CDI-2 total score and the 2 scales, i.e., emotional problems and functional problems, and will be summarized descriptively by treatment group and visit.

The CDI-2 total score will be categorized as follows:

1. Normal: Male Score < 22, Female Score < 21
2. Elevated: $22 \leq$ Male Score < 32, $21 \leq$ Female Score < 32
3. Very Elevated: Male or Female Score ≥ 32 .

	STATISTICAL ANALYSIS PLAN, Version 3.0
Protocol Number: ARQ-151-311	Sponsor: Arcutis Biotherapeutics, Inc.

The proportion of subjects that meeting the criteria will be summarized by treatment group and visit.

A summary of the shifts in CDI-2 category from baseline to each study visit will also be provided.

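### At ages 12 and over, post-baseline PHQ-8 and Modified PHQ-A are summarised only in five-point bands, so a small average rise would mostly stay inside a band; add score and change-from-baseline summaries, as the SAP already has for CDI-2

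*SAP*

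**What the plan says.** SAP section 2 lists PHQ-8 (adults) and Modified PHQ-A (ages 12-17) as safety endpoints. SAP 5.5 derives a total of 0-24 for each from eight items scored 0-3.

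SAP 13.5 sorts that total into five bands (0-4, 5-9, 10-14, 15-19, 20-24) and plans two outputs: "The number and percentage of subjects in each category will be summarized by treatment and visit", and "A summary of the shifts in depression category from baseline to each study visit will also be provided". It names no observed score and no change in score after baseline. SAP section 8 summarises PHQ-8 and PHQ-A scores at baseline only.

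Protocol exclusion 15 removes "Subjects with a PHQ-8 (adults) or modified PHQ-A (adolescents, 12-17 years old inclusive) score ≥10 at Screening or Baseline/Day 1 visits".

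For ages 6-11, SAP 13.6 is fuller: "The observed values and changes from baseline will be calculated for CDI-2 total score and the 2 scales", by treatment group and visit, and CDI-2 is also put into three categories with a shift table. Laboratory values (13.2), vital signs (13.3) and the investigator's skin-irritation score (13.4) are likewise summarised as continuous values; 13.2 and 13.3 name change from baseline.

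All safety analysis is descriptive (SAP section 13).

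**The concern.** Depression is a stated interest here. Protocol 2.3.7 reports psychiatric adverse events in 5.9% of patients on oral roflumilast against 3.3% on placebo and names depression among the most common. The PHQ instruments are completed at every visit.

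With entry capped at 9, a rise from 0 to 4, or from 5 to 9, is recorded as no change, while a rise from 4 to 5 counts as a shift. In a pre-screened, probably low-scoring sample, the two arms could differ by a small amount on average and the band tables could still look balanced. The score that would show the difference is already in the analysis dataset. SAP 13.5 gives no reason for treating PHQ differently from CDI-2.

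**Working it through.** The plan states no figure for the PHQ analysis, so there is nothing of its own to reproduce.

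**Inputs from the documents**
- Five bands, each 5 points wide (SAP 13.5); total 0-24 (SAP 5.5).
- Entry scores 0-9 (Protocol 4.5.2, exclusion 15). The SAP follows Amendment 4, which was not supplied; I assume the limit is unchanged.
- Referral thresholds 10 and 15 (Protocol 5.1.7 and 5.1.8).
- Randomisation 2:1.

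**Assumed, not in the documents**
- Baseline distribution on 0-9: uniform, or skewed with weights proportional to q^s, where q = m/(1+m) and m = 1, 2 or 4 (means after truncation 1.0, 1.8 and 2.8).
- Random change with SD 2 points.
- 300 or 450 subjects aged 12 and over.

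**Step 1: who stays in the same band after a rise of k points?**

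Band = floor(score/5). For a uniform baseline the share staying is (5 − k)/5. For the most skewed case (q = 0.5, k = 1) only scores 4 and 9 cross: the share crossing is (0.5^4 + 0.5^9)/1.998 = 0.0645/1.998 = 3.2%, so 96.8% stay.

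| Rise | Uniform | Mean 2.8 | Mean 1.8 | Mean 1.0 |
|---|---|---|---|---|
| 1 | 80% | 88% | 92% | 97% |
| 2 | 60% | 73% | 81% | 90% |
| 3 | 40% | 54% | 64% | 77% |
| 4 | 20% | 30% | 38% | 52% |
| 5 or more | 0% | 0% | 0% | 0% |

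Most subjects stay put at 1-2 points under every distribution tried. At 3-4 points it depends on the baseline, and from 5 points nobody stays. Because all start below 10, anyone who reaches 10 or 15 must change band.

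**Step 2: what does that cost in sensitivity?**

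In 2,000 simulated trials per setting (uniform and mean-1.8 baselines), follow-up = baseline + normal noise (SD 2) + effect on active, rounded and held within 0-24. A difference counts as picked up when z > 1.96, first for mean change and then for the share moving up at least one band.

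| Effect on active | Mean change | Upward band shift | Arm difference in upward shift |
|---|---|---|---|
| All rise 0.5 | 47-68% | 13-29% | 4-6 points |
| All rise 1 | 97-99.9% | 52-80% | 8-12 points |
| All rise 2 | about 100% | 99-100% | 20-27 points |
| 5% rise 8 | 31-53% | 13-28% | about 4-5 points |

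So the loss lies at average rises of about 1 point or less. At 2 points most individuals still stay in their band, but enough cross for the shift table to separate the arms.

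**Step 3: does the ranking survive another model?**

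Skewed count (gamma-Poisson) scores, 217 against 108 subjects (50% adults of 650, split 2:1), unadjusted mean change:
- Uniform 0.5-point rise: 86-94% for mean change against 16-19% for band shift in one set of runs. Another set gave 74% and 50% for mean change at baseline parameters 1.5 and 2.5. At 108 against 54 (the supplied protocol's 25% adult cap) these fell to 49% and 29%.
- 5-point rise in 10% of active subjects: the two were close in one set of runs; in the other, bands did better (63%/36% for mean change, 84%/52% for band shift).
- 8-point rise in 10%: 85%/66% against 85%/62%. In 5%: 34%/22% against 34%/21%.

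The score's advantage for small uniform shifts holds in both models. For concentrated worsening the ranking changes with the model.

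**The case against.** **The general rules may already cover this.** SAP 5.6 prescribes means and changes for continuous variables, Protocol 6.6 calls for descriptive statistics on quantitative safety data, and SAP 3.5 lists no departure for PHQ. This has some force: the sponsor may intend the tables. But neither rule names PHQ, and 13.2, 13.3 and 13.6 each spell out their change-from-baseline output while 13.5 specifies bands alone. One sentence would settle it.

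**The bands match what matters clinically.** The referral thresholds are band edges, and nobody can reach one without appearing in the shift table. That stands, and is why the band tables should stay. Nor does any document call an average drift of half a point meaningful.

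**CDI-2 is a weak comparator.** CDI-2 is banded too, and its entry limits (below 17 for girls, below 18 for boys) lie wholly inside its lowest category, so it needs the score more. PHQ at least has an edge at 5 inside its entry range. This is correct, but it explains why CDI-2 has a score summary, not why PHQ should lack one.

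**A stronger reading to resist.** A reader might infer that most of any depression signal would be hidden, or that the trial could wrongly report none at ages 12 and over. The documents do not support that. They give no PHQ distribution or expected effect, larger rises do show, and treatment-emergent adverse events (13.1) and the C-SSRS (13.7) are reported separately.

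**Conclusion.** The gap holds in a limited form and is minor. Post-baseline PHQ-8 and Modified PHQ-A are specified only in bands, and with entry below 10, rises of 1-2 points leave most subjects in the band where they started (60-97% under the distributions tried). Sensitivity to a uniform shift of about 1 point or less is clearly lower than the derived scores allow. Rises of 5 or more, and any subject reaching 10 or 15, remain visible. For worsening concentrated in a few subjects, no general advantage of the score can be claimed.

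All percentages rest on assumed baseline distributions, variability and numbers of subjects. Because safety is not formally tested, they describe how readily a difference would be noticed, not the power of a planned test. No efficacy conclusion and no error rate is affected.

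**What to change.** Add one sentence to SAP 13.5, for example: *PHQ-8 and Modified PHQ-A total scores, and their changes from baseline, will be summarised descriptively at each visit for each treatment group.* Keep the band counts and the shift table.

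A descriptive between-group difference in mean change with a 95% CI is optional. It goes beyond what 13.6 does for CDI-2, and section 13 rules out formal inference on safety.

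In the same edit, reconcile the missing-item rules: 13.5 sets the score to missing if any item is missing, whereas 5.5 prorates when one of the eight is missing.

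Cost: SAP wording and one table per instrument from scores already derived. No protocol amendment and no new data.

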13.6 Children's Depression Inventory 2 (CDI-2)

The CDI-2 Assessment will be performed in children subjects (6-11 years old, inclusive).

The observed values and changes from baseline will be calculated for CDI-2 total score and the 2 scales, i.e., emotional problems and functional problems, and will be summarized descriptively by treatment group and visit.

The CDI-2 total score will be categorized as follows:

1. Normal: Male Score < 22, Female Score < 21
2. Elevated: $22 \leq$ Male Score < 32, $21 \leq$ Female Score < 32
3. Very Elevated: Male or Female Score ≥ 32 .

	STATISTICAL ANALYSIS PLAN, Version 3.0
Protocol Number: ARQ-151-311	Sponsor: Arcutis Biotherapeutics, Inc.

The proportion of subjects that meeting the criteria will be summarized by treatment group and visit.

A summary of the shifts in CDI-2 category from baseline to each study visit will also be provided.

13.7 Columbia-Suicide Severity Rating Scale (C-SSRS)

The Columbia-Suicide Severity Rating Scale (C-SSRS) is a questionnaire used (for adolescents and adults 12 years old and older) for suicide assessment developed by multiple institutions, including Columbia University. The C-SSRS prospectively assesses Suicidal Ideation and Suicidal Behavior. At the Screening study visit, “Baseline/Screening” version of the C-SSRS will be used. This version assesses Suicidal Ideation and Suicidal Behavior during the subject’s lifetime and during the past 6 months. For the Screening visit, “lifetime” experience of the subject with Suicidal Ideation and Suicidal Behavior will be summarized. On all subsequent visits, the “Since Last Visit” version will be used (Baseline/Day 1, Week 1/Day 8, Week 2/Day 15 or Week 4/Day 29).

Tables will include results from the Suicidal Ideation and Suicidal Behavior sections of the C-SSRS. Frequencies and percentages of subjects with a response of “Yes” at any point on the Suicidal Ideation and Suicidal Behavior items will be summarized by study visit and treatment group.

13.8 Physical Examination

The number and percentage of subjects with normal and abnormal findings in the physical examination will be presented by body system and treatment group at each study visit.

14 PHARMACOKINETICS ANALYSIS

Concentration data will be summarized by visit by age group (<18 vs. ≥ 18) and overall, for active treatment group using descriptive statistics, reporting n, mean, standard deviation, median, Q1, Q3, minimum, and maximum, and geometric statistics including geometric mean and coefficient of variation. For computation of mean plasma concentrations, data that are below the limit of quantification (BLQ) will be set to 0.0001. The PK population will be used for these analyses.

PK data will be presented in the listing.

	STATISTICAL ANALYSIS PLAN, Version 3.0
Protocol Number: ARQ-151-311	Sponsor: Arcutis Biotherapeutics, Inc.

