To assess the safety of Roflumilast cream 0.15% vs vehicle administered once daily (QD) x 4 weeks to individuals 6 years of age and older with AD	
 Incidence and severity of adverse events (AEs) Changes and percent change in clinical laboratory results Changes and percent change in vital signs The subject incidence of >5% weight loss or gain on study Local tolerability assessments Patient Health Questionnaire depression scale (PHQ-8) and Modified PHQ-9 for Adolescents (PHQ-A) Children's Depression Inventory 2nd Edition (CDI-2) Columbia-Suicide Severity Rating Scale (C-SSRS)
Pharmacokinetic	
To assess the systemic exposure of roflumilast and its N-oxide metabolite following Roflumilast cream 0.15% QD application x 4 weeks	
 Plasma concentrations of roflumilast and its N-oxide metabolite

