h Adolescents and adults will complete the C-SSRS (12 years of age and older). Adults will complete the PHQ-8. Adolescents (ages 12 to 17, inclusive) will complete the PHQ-A (PHQ-9 modified). Parents/caregivers will complete CDI-2 (parent report) for children 6-11 years of age, inclusive.

i The DLQI will be completed by subjects ≥ 17 years of age. The CDLQI will be completed for subjects 6 to 16 years old, inclusive. The Dermatitis Family Impact Questionnaire (DFI) will be completed by parents/caregivers for all subjects 6 to ≤ 17 years of age.

j Photography of AD lesion(s) selected by the Investigator will be performed at all investigational sites. All efforts will be made to de-identify the subjects. Canfield equipment will be used to capture photographs. Subjects who are unwilling to participate in the medical photography will be allowed to opt out of this procedure, as documented on the Informed Consent Form.

	STATISTICAL ANALYSIS PLAN, Version 3.0
Protocol Number: ARQ-151-311	Sponsor: Arcutis Biotherapeutics, Inc.

^k A urine pregnancy test will be administered to all females of child-bearing potential. A negative result is required for continued participation in the study, and results must be available prior to dispensing of study drug at each visit.

^l For all subjects entering this study under Amendment 2, a single PK trough draw will be collected at Day 29 only for subjects \geq 12 years old. Ensure study medication was not applied in the area where PK will be drawn.

^m Subjects to apply assigned IP during clinic visits, except for the Day 29/ET visit.

ⁿ It is expected that kits will be dispensed based on %BSA affected. See IP Handling Manual for details.

^o On Day 8 and 15, dispensing of IP is optional. Site should review IP kit to ensure sufficient IP is available until the next visit and only dispense additional IP if needed. On Day 29, if the subject is unable to perform the Day 29 clinic visit due to COVID-19 restrictions (isolation, quarantine, etc.) then additional IP may need to be dispensed so IP can continue to be applied at home until the subject is able to return to the clinic to complete the Day 29 assessments (see IP Handling Manual for the process to dispense additional IP at or after Day 29).

^p Every tube should be weighed and recorded when dispensed and returned. See IP Handling Manual for details.

^q Compliance determination is described in the IP Handling Manual

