4.8 Pharmacokinetic (PK) Population

Pharmacokinetic population will include all subjects receiving the active drug with quantifiable plasma concentrations of roflumilast.

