5.6 Descriptive Statistics

All continuous variables will be summarized by presenting the number of subjects, mean, standard deviation (SD), median, Q1, Q3, minimum, and maximum. For PK endpoints, geometric statistics including geometric mean and coefficient of variation (CV) will also be provided.

Categorical variables will be presented as frequencies and percentages.

Summary tables will be presented by visit, when applicable.

Change from baseline will be calculated as:

	STATISTICAL ANALYSIS PLAN, Version 3.0
Protocol Number: ARQ-151-311	Sponsor: Arcutis Biotherapeutics, Inc.

Assessment value at postbaseline visit X – baseline value.

Percent change from baseline will be calculated as:

$$(\text{Assessment value at postbaseline visit X} - \text{baseline value}) \times 100\% / (\text{baseline value})$$

Percent change from baseline will be missing in situation where baseline value equals to 0.

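### The unit-less 0.0001 substituted for BLQ concentrations is unsuitable for the geometric mean and CV, which in practice concerns the N-oxide summaries

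*SAP*

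**What the plan says.** For the calculation of mean concentrations, the rule in SAP section 14 is that "data that are below the limit of quantification (BLQ) will be set to 0.0001". The sentence before it lists the statistics to be reported, by age group (under 18, and 18 or over) and overall. They are n, mean, SD, median, quartiles, minimum and maximum, together with "geometric statistics including geometric mean and coefficient of variation". SAP section 5.6 repeats the requirement: "For PK endpoints, geometric statistics including geometric mean and coefficient of variation (CV) will also be provided".

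Three other places fix what the rule can act on:

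- The endpoint covers two analytes (SAP section 2): "Plasma concentrations of roflumilast and its N-oxide metabolite".
- SAP section 14 adds: "The PK population will be used for these analyses". SAP section 4.8 defines that set through the parent drug alone: "Pharmacokinetic population will include all subjects receiving the active drug with quantifiable plasma concentrations of roflumilast".
- Each subject gives one sample. The PK footnote to the schedule in SAP section 3.2 says that "a single PK trough draw will be collected at Day 29 only for subjects" aged 12 or over, for those entering under Amendment 2.

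Neither document gives a unit for 0.0001, an LLOQ, a formula for the CV, a limit on the BLQ share, or a requirement to report how many values were BLQ. Protocol section 6.15 plans only arithmetic descriptive statistics and has no BLQ rule.

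**The concern.** In an arithmetic mean, 0.0001 behaves like zero and does no harm. On the log scale it lies far below any plausible concentration, so each substituted value pulls the geometric mean down and greatly widens the log variance. The size of the pull depends on the unit in which concentrations happen to be tabulated, which should not affect a relative summary.

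What is at stake is the exposure summary for the N-oxide, a named PK endpoint that protocol section 2.1 calls the active metabolite. The table is split by age group. If the two age groups had different BLQ shares, their geometric means could differ for a reason that owes more to the constant than to exposure.

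**Working it through.** There is no PK figure in the plan to reproduce, so this is a sensitivity calculation.

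**Which values the rule reaches.** With one sample per subject, a BLQ roflumilast value normally places the subject outside the PK population, so there is little or no parent value left to substitute. Membership does not depend on the N-oxide. A subject with quantifiable roflumilast and BLQ N-oxide is in the set, and that N-oxide value is substituted.

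**Inputs.** From SAP section 14: c = 0.0001. Assumed, because the documents give none of these: geometric mean of the quantifiable values G = 0.1 to 1000 in the reporting unit, geometric CV of those values 100%, and BLQ share f = 1% to 5%.

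**Formulas** for a log-normal sample with a fraction f set to c:

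- d = ln(G) − ln(c)
- geometric mean ratio (reported / quantifiable only) = exp(−f·d)
- s² = ln(1 + 1²) = 0.693
- log variance v = (1 − f)·s² + f(1 − f)·d²
- geometric CV = √(exp(v) − 1)

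**Worked case, G = 1.** d = ln(10000) = 9.21 and d² = 84.83.

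- f = 1%: ratio = exp(−0.0921) = 0.912. v = 0.99 × 0.693 + 0.0099 × 84.83 = 1.526, so the geometric CV = 190%.
- f = 5%: ratio = exp(−0.4605) = 0.631. v = 0.95 × 0.693 + 0.0475 × 84.83 = 4.688, so the geometric CV = 1037%.

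**Range over G**

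| G (reporting unit) | f = 1%: ratio, geometric CV | f = 5%: ratio, geometric CV |
|---|---|---|
| 0.1 | 0.933, 148% | 0.708, 420% |
| 1 | 0.912, 190% | 0.631, 1037% |
| 10 | 0.891, 253% | 0.562, 3236% |
| 1000 | 0.851, 500% | 0.447, 66469% |

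The rows for G = 1 and G = 1000 can be read as the same data in two units a factor of 1000 apart. At 5% BLQ the fall is 37% in one and 55% in the other. Starting from a geometric CV of 50% or 150% in place of 100%, the value at G = 1 and 1% BLQ is 137% or 254%.

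**Arithmetic statistics, f = 5%, CV 100%.** The mean ratio is 0.950. The arithmetic CV is √(0.95 × 2 − 0.95²) / 0.95 = 105%.

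**Age-group contrast, G = 1.** With identical quantifiable distributions but 1% BLQ in one group and 5% in the other, the geometric means differ by exp(0.04 × 9.21) = 1.45.

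**LLOQ-based substitution for comparison.** Assume LLOQ = G/10 and substitute LLOQ/2 = G/20, so d = ln(20) = 3.00. At 1% BLQ the ratio is 0.970 and the geometric CV 108%; at 5% BLQ they are 0.861 and 140%. The age-group factor becomes exp(0.04 × 3.00) = 1.13. None of these depends on the reporting unit.

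**The case against.** **The rule may not cover the geometric mean.** It refers to mean concentrations, and nowhere says that it covers the geometric mean or the CV. That is correct: applying it there is an inference. It is a strong one, because the text makes no exception and a small positive number in place of zero has a purpose only if logs are taken. If the sponsor intends the arithmetic mean alone, the SAP has no BLQ rule for the geometric statistics, and the sentence still needs editing. The CV also has no stated formula; if it is arithmetic, it barely changes.

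**The rule has little to act on.** A reader might infer that both analytes are distorted. The PK population definition does not support that. For roflumilast the rule is close to idle, and for the N-oxide nothing in the documents shows that BLQ values occur in subjects with quantifiable parent drug.

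**The larger figures are not forecasts.** A reader might take the 5% row as expected. It does not follow from the assumed distribution. With G = 1, log SD √0.693 = 0.833 and an assumed LLOQ of 0.1, the share below LLOQ is Φ(−2.303 / 0.833) = 0.28%. That gives a geometric mean ratio of exp(−0.0028 × 9.21) = 0.974, a fall of about 3%, and a geometric CV of about 124%. Five percent BLQ would need a separate cluster of very low N-oxide values. Subjects who did not apply the cream are one source, but their parent drug would probably be BLQ too, and they would then be outside the set. This objection stands in full.

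**Nothing depends on these statistics.** PK is descriptive, with no test. The median and quartiles in the same table are hardly affected by a few BLQ values, and individual values are listed. This also stands. What remains is that the written rule is unsuitable for log-scale statistics wherever it applies.

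**Conclusion.** The concern holds in a narrow form and is minor. As written, SAP section 14 lets a constant with no unit and no LLOQ link enter the geometric mean and geometric CV, in practice for the N-oxide only. The size is conditional. It is nil if no N-oxide value in the PK population is BLQ. At 1% BLQ the geometric CV is the statistic seriously affected (100% to 190% at G = 1), while the geometric mean falls by only about 9%. A large fall in the geometric mean needs a BLQ share nearer 5%, which the documents give no reason to expect. All of this rests on assumed values for G, the CV, the unit and the BLQ share.

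Two stronger conclusions might be drawn and are not supported. One is that the exposure summaries as a whole would reflect the constant and not the drug; the parent-drug summary is almost untouched and the N-oxide effect may be zero. The other is that a trial conclusion is at risk; no efficacy or safety inference uses these statistics.

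**What to change.** In SAP section 14, keep 0.0001 out of the log-scale statistics. Suggested wording:

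*For the geometric mean and geometric CV, BLQ values are replaced by a value tied to the assay LLOQ (for example LLOQ/2). These two statistics are not reported for an analyte and age group in which the BLQ share exceeds [pre-stated limit]. The number and percentage of BLQ values are reported by analyte and age group. The geometric CV is √(exp(variance of the log concentrations) − 1).*

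State the concentration unit and the LLOQ of each analyte in the table footnote. The roflumilast BLQ count has to be taken over all active-arm subjects with a sample, because within the PK population it is zero or nearly so by construction.

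The arithmetic mean can keep the present constant or use zero without visible difference. LLOQ/2 and the cut-off are conventions. Substitution at LLOQ/2 reduces the distortion without removing it (still a 14% fall at 5% BLQ in the comparison above), which is why the limit and the counts belong with it.

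The cost is a few SAP sentences, a footnote and a small programming change. No new data are needed.
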